6.5 Time Windows

| Visit | Time Windows allowed |
|-----------|---|
| Screening | N/A |
| Baseline | N/A |
| Diet 1 | After exactly 7 days adherence to consecutive study diet. |
| Washout | Begins on the first day after Diet 1 is completed and is no fewer than 7 days. |
| Diet 2 | After exactly 7 days adherence to consecutive study diet and no fewer than 7 consecutive days of not adherence to a study diet. |
| MRI | After no fewer than 7 consecutive days of not adherence to a study diet. |

7 General Analysis Considerations

7.1 Timing of Analyses

The final analysis will be performed after all imaging data and labs has been processed.

8 Summary of Study Data

All continuous variables will be summarized using the following descriptive statistics: n (non-missing sample size), mean, standard deviation, median, maximum and minimum. The frequency and percentages (based on the non-missing sample size) of observed levels will be reported for all categorical measures. In general, all data will be listed, diet and subject, and when appropriate by visit number within subject. All summary tables will be structured with columns.

8.1 Demographic and Baseline Variables

Demographics will be assessed at baseline to confirm all participants adhere to inclusion/exclusion criteria prior to enrollment.

8.2 Treatment Compliance

Treatment compliance verification will include KSP check in with participants during diet intervention as well as quality checks of data and lab results.

9 Efficacy Analyses

All efficacy variables will be listed by subject within study center. Data will be summarized by treatment group. N, Mean, Standard Deviation, Minimum and Maximum will summarize continuous efficacy variables, whereas number and percent will summarize categorical efficacy variables.

All analyses of the continuous efficacy variables (e.g. salt sensitivity) will be performed as analysis of variance with treatment group adjusting for study center and surgical category. Treatment groups will be tested at the 2-sided 5% significance level.

All assumptions for regression models will be assessed by viewing plots of the residual values.

9.1 Primary Efficacy Analysis

Define the primary analysis that will provide the main result of the trial in this section. Note the use of “analysis” singular. This section of the document should be structured in parallel with 5.2 in terms of the ordering of endpoints considered. If appropriate use standard text: “The summary statistics will be produced in accordance with section 9.”

10 Safety Analyses

Per-protocol all randomized subjects who have been gone through diet intervention in the study without major protocol deviations that may significantly impact the interpretation of efficacy results. Detailed protocol deviation criteria will be determined at the latest before database lock. Data will be used for the primary efficacy outcome and safety analysis. Subjects enrolling in study need to satisfy all the following basic criteria: (1) Meet all the eligibility criteria specified in the study protocol; (2) The subjects were randomized and received the assigned interventions. (3) Adverse Events

When calculating the incidence of adverse events, or any sub-classification thereof by treatment, time period, severity, etc., each subject will only be counted once and any repetitions of adverse events will be ignored; the denominator will be the total population size.

Only incidence of AEs that are judged to be related to the treatment will be reported.

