8.0 Study Withdrawal/Discontinuation

Subjects may withdraw from the study at any time and should notify study personnel if they wish to withdraw from the study. Subjects may request their biological samples to be destroyed at any time. However, any data or biological samples that have already been used for research cannot be destroyed. Subjects may be discontinued from the study at the discretion of the investigators' (possible reasons listed below). Subjects will receive financial compensation for the visits that they complete.

Possible reasons for withdrawal/discontinuation from study include, but are not limited to:

- Noncompliance with treatment or procedures
- Decision by participant/participant withdraws consent
- Lost to follow-up
- Starting a medication that would exclude the subject (see exclusion criteria)
- Development of a significant medical condition specified in the exclusion criteria
- In female subjects, becoming pregnant during study
- Significant adverse event deemed by investigator to preclude continued participation

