10.0 Privacy/Confidentiality Issues

Strict confidentiality will be maintained to the fullest extent by the research team, including keeping all data in a secure, locked cabinet with limited access and/or password protected databases, i.e. REDCap. All specimens will be coded after they are obtained and the code key kept in a locked cabinet. Blood samples will be coded anonymously to remain confidential and identifiers will be kept in a separate, secure, locked location. Samples may be shared with third parties outside of Vanderbilt for future testing but will remain anonymous to the recipient. If samples are accidentally lost, subjects will not be re-contacted to provide a substitute sample. The investigators will not be obligated to keep contact information to re-contact the subject. Subjects may contact the principal investigator at any time to request that samples be destroyed.

The data files generated by the MRI scanner and L-Dex software are coded using a project name and unique number generated sequentially. Only the investigators will have the key to the subject codes. Image analysis will use the coded files. The safety surveys described above include questions about sensitive health issues. This information will remain with the signed

consent form in a secured area near the scanner. These records will remain in the investigators' possession for ten years following the termination of the study and will then be destroyed.

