6.3 Randomization and Blinding

All subjects will undergo the same interventions. However, the order of the study interventions will be randomized using a randomized crossover design.

This is not a blinded study.

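### One per-protocol set serves both the primary outcome and safety, its major-deviation criteria stay open until database lock in an unblinded study, and no all-evaluable analysis stands beside it

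*SAP*

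**What the plan says.** The only analysis set in either document is in SAP section 10, under the safety heading: "Per-protocol all randomized subjects who have been gone through diet intervention in the study without major protocol deviations". Its use is stated as: "Data will be used for the primary efficacy outcome and safety analysis". No major deviation is listed; instead, "Detailed protocol deviation criteria will be determined at the latest before database lock". The same section takes the whole population as the denominator for adverse-event incidence.

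SAP 9.1, where the primary analysis should be defined, still holds template instructions.

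On who can see what:
- SAP 6.3: "This is not a blinded study".
- Protocol 10.0: "Image analysis will use the coded files". The same paragraph leaves the key to the subject codes with the investigators.
- SAP 7.1: "The final analysis will be performed after all imaging data and labs has been processed".

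On adherence:
- SAP 8.2: "Treatment compliance verification will include KSP check in with participants during diet intervention as well as quality checks of data and lab results". It gives no numerical threshold.
- SAP 6.5 fixes seven days on each diet, at least seven days of washout and at least seven off-diet days before MRI. It does not say which departures are major.
- Protocol 8.0 allows discontinuation at the investigators' discretion. Its listed reasons include noncompliance and a significant adverse event.

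**The concern.** Fixing deviation criteria before lock protects a trial when those who write the criteria cannot see outcomes by group. Nothing here secures that. Pressures are recorded at each visit, so salt-sensitivity status can be worked out once both diets are done. Sodium values come from coded files, but the code can be opened by the people likely to judge deviations. No blinded deviation review is described, and the documents do not place database lock before or after image processing.

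With about 40 participants, one or two exclusions can move a p-value across 0.05. With no companion analysis, a reader of the results could not tell whether they had.

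Safety is a separate matter. A set limited to people who went through the diets without major deviations can omit those who stopped because a diet harmed them.

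**Working it through.** **1. The plan's own figure.** SAP Aim 1 gives a difference of 6 mmol/L, SD 4, 20 per group, two-sided 0.05 and power of at least 80%. By the normal approximation:

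power = Φ(6 / (4 × √(2/20)) − 1.96) = Φ(4.74 − 1.96) = Φ(2.78) = 99.7%.

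The exact noncentral-t value is 99.6%. With 10% excluded (18 per group) it is 99.2%. The stated power is met, and exclusions do not threaten it on these inputs. The issue is type I error and bias.

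**2. What would have to be known.** The Aim 1 test compares tissue sodium between groups formed from the pressure response. Under the null hypothesis sodium is unrelated to that response, so exclusions chosen on pressure alone leave the type I error of the sodium test at its nominal level. Inflation requires the sodium values too. That is why the investigators' hold on the key matters.

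**3. Upper bound.** Both groups were simulated from the same normal distribution, several thousand data sets per setting. The k participants least favourable to the observed direction were removed and the test was repeated at 0.05.

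| Setting | k = 1 | k = 2 | k = 3 |
|---|---|---|---|
| 30/10, t-test | 13% | 25% | 40% |
| 30/10, Mann-Whitney | 13% | 24% | 39% |
| 20/20, Mann-Whitney | 10% | 18% | 28% |

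With no removals the rate was 4 to 5%. Repeat runs put three removals at 30/10 with the t-test between 40% and 43%. The 20/20 split is the SAP's. The 30/10 split is an assumption, close to applying the 74% prevalence in Protocol 1.0 to 40 people (0.74 × 40 = 29.6).

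**4. Milder flexibility.** Here the rules drop people without regard to sodium, and the more favourable result is kept (Mann-Whitney).
- Full set or one rule dropping 1 to 3 at random (30/10): about 6%.
- Full set or four rules, each dropping 4 of 40 (20/20): about 9%.
- Full set or nine such rules (20/20): about 13%.

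The documents give no number of exclusions or of candidate rules, so these too are assumed scenarios.

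**5. Safety.** Three statements do not fit together. Protocol 8.0 lists a significant adverse event as a reason to discontinue. SAP section 10 restricts the safety set to those who went through the diets without major deviations. The same section divides by the whole population. A participant who stops for an adverse event can be missing from the numerator yet counted in the denominator. No calculation is needed.

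**The case against.** Several points on the other side are sound.

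- Database lock is the latest date for the criteria, not the planned one, and setting them before lock is common practice. SAP 7.1 describes only a final analysis. A reader might infer that exclusions can be chosen once the results are visible. The documents do not support that: they describe no earlier test, and what may be available is accumulating participant-level data.
- Coded image files are a real, though partial, safeguard. Pressures are recorded by a nurse, and nothing says who computes the pressure change or when.
- The larger simulated rates need deliberate selection on sodium value. Real deviation rules act on diet days, urine collection or timing.
- Adherence rules are partly fixed already in SAP 6.5.
- The primary outcome attached to the per-protocol set is never named. The Aim 1 text does not itself mention a per-protocol limit, and the secondary Aim 1 regression is described as covering all participants. That regression still has no defined set.
- Salt sensitivity cannot be assigned without both diet periods, so conventional intention-to-treat does not fit. People who did not follow the diets may be misclassified, which is a fair argument for keeping a per-protocol result.

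These points limit the claim about type I error. They do not supply the missing criteria, a blinded review or a companion analysis. The whole-population denominator does not rescue the safety set either; it adds a conflict that must be reconciled.

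**Conclusion.** The point holds in two parts.

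**Primary outcome.** The plan combines one per-protocol set, unlisted major-deviation criteria, no blinding, access to the code key and no all-evaluable analysis. Bias is possible, not shown. The worst case is about 10%, 18% or 28% false positives at the SAP's 20/20 with Mann-Whitney, or 13%, 25% or 40% at an assumed 30/10 with a t-test, for one, two or three deliberate removals. About 6 to 9% is a fairer figure for a few alternative rules applied without regard to sodium. A reader might take the larger figures as the expected error of this study. They are not, because they assume intent and linked data that the documents do not describe.

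**Safety.** The set is wrong as written, whatever view is taken of the first part.

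A reader might also infer that the all-evaluable set has to be primary. That does not follow: it retains people whose non-adherence may misclassify their salt sensitivity, so the choice is a trade-off. What is required is that both results appear and that the primary one is named in advance.

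**What to change.** 1. Analyse safety in all participants who started a study diet, and use that number as the denominator.
2. List the major-deviation criteria in the SAP now, before sodium values are linked to salt-sensitivity status. Build them from rules already in the documents: the diet, washout and off-diet intervals in SAP 6.5 and the scheduled 24-hour urine collections.
3. Report the Aim 1 comparison in all participants with both diet-visit pressures and a sodium MRI, beside the per-protocol result.
4. Replace the template text in SAP 9.1 with a statement of the primary outcome and of which of the two sets is primary, and move the set definitions out of the safety section.

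The cost is SAP wording and one extra analysis. The downside is that the all-evaluable result includes some non-adherent participants. No stated sample size or power figure changes.

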2.0 Rationale and Specific Aims

The following hypotheses and specific aims were designed in response to a recent call from the American Heart Association (AHA) for i) standardized biomarkers to enable the clinical diagnosis of SSSB and ii) improved understanding of human tissue salt storage mechanisms²⁵.

Hypothesis 1: Tissue sodium content is elevated in adults predisposed for SSSB; tissue sodium and adiposity provide biomarkers for SSSB. **Aim 1:** Black adults without hypertension (20 male; 20 female) with BMI range=18 to 40 kg/m² and age range=18-55 years will be assessed for SSSB according to recent guidelines²⁶, and scanned using MRI to quantify tissue sodium and fat fraction in the lower extremities. Multivariable analyses will be applied to quantify relationships between tissue sodium, fat fraction as a surrogate of BMI, age, and sex with SSSB status. **Impact.** Unique tissue sodium and fat profiles may provide internal, mechanistic biomarkers of SSSB that could be used as endpoints in clinical trials of SSSB.

Hypothesis 2: Tissue sodium content is elevated in tissues affected by impaired lymphatic flow in adults with SSSB. **Aim 2:** The same participants will be scanned using noninvasive MR lymphangiography to quantify lymphatic flow velocity in the lower extremities. Non-parametric tests will be applied to evaluate the association between lymphatic flow and tissue sodium content in adults evaluated for SSSB. **Impact.** Identifying the extent of lymphatic dysfunction in SSSB could motivate novel treatment strategies to improve lymphatic pumping and tissue sodium clearance.

Hypothesis 3: Elevated tissue sodium content is associated with reduced renal perfusion in adults with SSSB. **Aim 3:** The same participants will be imaged using noninvasive MR spin-labeling techniques to measure kidney perfusion (ml blood/100g

tissue/min). Non-parametric tests will be applied to evaluate the association between kidney perfusion and peripheral tissue sodium content in adults evaluated for SSBP. Impact. Imaging of renal cortical circulation, where sodium-filtering nephrons are located, related to tissue sodium stores in SSBP may have potential to portend salt sensitive hypertension.

The overall goal of this work is to provide noninvasive imaging tools to assess a more complete spectrum of mechanisms underlying SSBP, which will motivate the use of these tools in future clinical trials to evaluate risk of SSBP or therapies to modify tissue sodium storage.

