3.0 Inclusion/Exclusion Criteria

Inclusion criteria will include identification as black race, age between 18 and 55 years, and BMI between 25 and 40 kg/m². Additionally, subjects must be normotensive or pre-hypertensive adults who are willing to adhere to study diets and who are able to provide informed consent.

The following exclusion criteria will apply:

- Prevalent cardiovascular disease or use of medications for cardiovascular disease
- Current or prior history of hypertension or use of blood pressure lowering medications
- Current or prior history of diabetes mellitus or use of anti-diabetic medications
- Prevalent renal disease (eGFR < 60 ml/min/1.73m²), abnormal serum sodium or potassium
- Current or prior smoker
- Current pregnancy
- Current steroid use
- Contraindications to MRI
- Persons who are deemed clinically unsuitable for an MRI by their treating physician and/or VUIIS MRI technologist
- Severe claustrophobia
- Open wounds on the top of the feet or hands or at locations of interest for measurement of bioimpedance and tissue dielectric.

Also excluded are subjects incapable of giving informed written consent:

- Subjects who are non-English speaking
- Subjects who cannot adhere to the experimental protocols for any reason, or have an inability to communicate with the researcher.
- Subjects who have limited mental ability to give informed consent, mentally retarded, altered mental status, mental disability, confusion, or psychiatric disorders.
- Prisoners

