9.0 Statistical Considerations

Subjects who are overweight or obese (n=20) will be recruited through this IRB. To analyze study hypotheses, and for comparison to normal weight individuals, we will share data from the study cohort of [name] (IRB #151943). This will include identical data acquired from at least n=20 subjects who are normal weight (18 to <25 kg/m²) and who meet identical inclusion/exclusion criteria.

Statistical analysis procedures for Aim 1: Statistical analyses will be performed by key study personnel and members of the Center for Quantitative Sciences at the VUMC. The primary statistical objective of Aim 1 is to test the hypothesis that adults who are salt sensitive have higher baseline tissue sodium relative to adults who are not salt sensitive. To test this, we will divide participants into those who are salt sensitive (SS, ≥5 mmHg change in mean arterial pressure ΔMAP following high salt diet compared to low salt diet) or not salt sensitive (NSS, <5 mmHg ΔMAP), according to a review of methods and recommendations from Kurtz et al.²⁶. The metric ΔMAP represents a continuous variable of SSBP. A Mann Whitney U test will be applied to determine whether tissue sodium content is significantly different in SS and NSS groups. Based on a prior study of tissue sodium storage in adults who are hypertensive (n=10)

or normotensive (n=12)¹⁹ we anticipate a similar difference in tissue sodium of 6±4 (mean ± standard deviation, mmol/L) between SS and NSS adults. Our study is designed to provide at least 80% power to detect differences in tissue sodium with a two-sided significance of p<0.05.

Our secondary statistical objective of Aim 1 is to test the hypothesis that tissue sodium content and potential risk factors for SSBP, including biological sex, age, and tissue fat/water fraction as a sensitive surrogate of BMI, are related to Δ MAP as a continuous variable. We will apply multivariable regression analysis using tissue sodium, fat/water fraction, biological sex, and age as independent variables, and Δ MAP as the dependent variable among all participants. With a sample size of 40 , we should be able to evaluate the four predictors of Δ MAP (each with one degree of freedom) without over-fitting the model.

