(see mentor support letter). The primary statistical objective of Aim 1 is to test the hypothesis that adults who are salt sensitive have elevated baseline tissue sodium relative to adults who are not salt sensitive. To test this, we will apply a previously-published, informed cutoff to dichotomize participants into those that are salt sensitive (SS, ≥ 5 mmHg reduction in Δ BP depletion) or salt resistant (SR, < 5 mmHg reduction in Δ BP), according to a review of methods and recommendations from Kurtz *et al.*¹¹. The metric Δ BP represents a continuous variable of SSBP; tests for normality and homoscedasticity will be made. Depending on normality, a Mann Whitney U test or a Student's t-test will be applied to determine whether muscle sodium content is significantly different in SS and SR groups, matched for race and accounting for biological sex as a covariate. Based on a prior study of tissue sodium storage in adults with hypertension (n=10) and normotensive (n=12)²⁶ we anticipate a similar difference in tissue sodium of 6 ± 4 (mmol/L) between SS and SR adults. With a sample size of 20 in each group, our study design will provide at least 80% power to detect differences in tissue sodium with a two-sided significance of $p<0.05$.

Our secondary statistical objective of Aim 1 is to test the hypothesis that muscle sodium content and potential risk factors for SSBP, including biological sex and tissue fat/water fraction as a sensitive surrogate of BMI, are related to Δ BP as a continuous variable. We will apply multivariate regression analysis using muscle sodium, fat/water fraction, and biological sex as independent variables, and Δ BP as the dependent variable among all participants. With a sample size of 40, we will have sufficient power to evaluate three predictors of Δ BP at the

Statistical analysis procedures for Aim 2:

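### The SAP's analysis-set rule (BMI 25–40, randomised in this study) shuts out the shared normal-weight cohort that the planned n=40 depends on; the two must be reconciled

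*SAP*

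**What the plan says.** **Who may be analysed.** SAP Section 10 starts from "Per-protocol all randomized subjects who have been gone through diet intervention in the study without major protocol deviations". It adds that subjects must "Meet all the eligibility criteria specified in the study protocol" and that "The subjects were randomized and received the assigned interventions". Although the heading is Safety Analyses, the text gives the set a wider use: "Data will be used for the primary efficacy outcome and safety analysis".

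**The eligibility criteria.** Protocol 3.0 requires "BMI between 25 and 40" kg/m². The list in SAP 6.2 also starts at 25; its upper limit is garbled in the supplied text, but only the lower limit matters here.

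**Who is meant to be analysed.** Protocol 2.0 describes Aim 1 as "Black adults without hypertension (20 male; 20 female) with BMI range=18 to 40" kg/m². Protocol 4.0 enrols 20 people here. Protocol 9.0 describes these 20 as overweight or obese and adds data on at least 20 others from IRB #151943, described as "subjects who are normal weight (18 to <25 kg/m²) and who meet identical inclusion/exclusion criteria". Protocol 9.0 then bases its four-predictor regression on 40 participants. SAP 6.1 uses the same total: "With a sample size of 40, we will have sufficient power to evaluate three predictors". The SAP text supplied does not mention the shared cohort.

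**The concern.** The analysis-set rule and the analysis sample size cannot both be followed. Half of the planned 40 have a BMI below the eligibility floor and were not randomised in this study. The SAP is the document that should settle who is analysed before the data are seen. As it stands, an analyst must either set aside the SAP's only stated population rule or drop the whole normal-weight cohort, and could make that choice after seeing results.

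If the rule were followed, three things would change whatever the salt-sensitivity split. The comparison with normal-weight individuals promised in Protocol 4.0 and 9.0 would disappear. The fat/water fraction, used as a surrogate for BMI, would be observed only in overweight and obese adults. The regressions planned on 40 would run on 20 at most.

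**Working it through.** **1. Reproduce the plan's n.** 20 enrolled here (Protocol 4.0, 9.0) + at least 20 shared (Protocol 9.0) = at least 40. This matches the 40 in Protocol 9.0 and SAP 6.1.

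**2. Apply the SAP Section 10 rule.**

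| Source | BMI (kg/m²) | Meets BMI 25–40? | Randomised in this study? | n kept |
|---|---|---|---|---|
| Enrolled here | 25–40 | yes | yes | at most 20 |
| Shared, IRB #151943 | 18 to <25 | no | no | 0 of at least 20 |

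The BMI ranges do not overlap, so the set holds 20 + 0 = 20 at most. Withdrawals and major deviations would lower it further. For the same reason, the statement in Protocol 9.0 that the shared participants meet identical criteria cannot be true of BMI.

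**3. Participants per regression predictor.**
- Protocol model (sodium, fat/water fraction, sex, age): 40/4 = 10 falls to 20/4 = 5.
- SAP model (sodium, fat/water fraction, sex): 40/3 = 13.3 falls to 20/3 = 6.7.

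**4. Power for the Aim 1 group comparison.** Inputs: difference 6 and SD 4 mmol/L, two-sided 0.05 (Protocol 9.0, SAP 6.1). Taking 4 as the within-group SD, d = 6/4 = 1.5. For the t-test, the noncentrality is 1.5/√(1/n₁ + 1/n₂) with n₁ + n₂ − 2 degrees of freedom. Mann-Whitney power is simulated with normal data and the exact test, so its second decimal varies slightly between runs.

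The plan's own figure comes first. At 20:20 the noncentrality is 1.5/√(0.05 + 0.05) = 4.74, giving t-test power 0.996 (Mann-Whitney about 0.995). The claim of at least 80% is amply met.

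At n = 20:

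| Salt sensitive : not | Noncentrality | t-test | Mann-Whitney |
|---|---|---|---|
| 10:10 | 3.35 | 0.89 | 0.85–0.86 |
| 13:7 | 3.20 | 0.86 | 0.82 |
| 14:6 | 3.07 | 0.83 | 0.77–0.78 |
| 15:5 | 2.90 | 0.78 | 0.71–0.72 |

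**5. Which split is plausible.** The background sections quote 74% salt sensitivity in black American adults and up to 50% in normotensive people. Neither figure is specific to normotensive black adults, so the split is an assumption. At n = 20, 50% gives 10:10 and 74% gives 0.74 × 20 = 14.8, about 15:5. Averaged over binomial splits of 20, t-test power is 0.87 at 50%, 0.85 at 60% and 0.75 at 74%. For comparison, 74% of the full 40 gives about 30:10, with t-test power 0.979.

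**The case against.** **The intent to pool is explicit.** Protocol 4.0 and 9.0 both say the shared data will be used to analyse the study hypotheses, and Aim 1 states BMI 18 to 40. This stands. It makes actual loss of half the sample unlikely, but it does not change what the SAP rule says.

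**The rule may cover only people enrolling here.** The eligibility list in SAP Section 10 is introduced as applying to subjects enrolling in the study, and Protocol 4.0 uses the word enrol only for the 20 recruited here. On that reading the BMI criterion does not touch the shared cohort. But the sentence that creates the set already confines it to subjects randomised in the study, so the shared cohort remains outside and n is still 20.

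**The SAP section is unfinished.** Section 9.1 still holds template instructions, and the list in Section 10 ends with an item that is not a criterion. This is fair, and it argues against treating the sentence as a considered decision. It also means that the supplied SAP has no competing population definition for the primary outcome.

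**The word identical evidently means otherwise identical.** Probably so, since the same sentence in Protocol 9.0 states the different BMI range. That part of the point is editorial.

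**A stronger reading on power.** A reader might infer that at n = 20 the stated 80% is lost, or survives only with nearly equal groups. The figures do not support this: 13:7 passes under both tests and 14:6 passes under the t-test. A reader might also infer that losing the shared cohort deletes one arm of the Aim 1 test. It does not, because the SAP's 20 per group refers to salt-sensitive and salt-resistant participants, not to weight classes.

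**Conclusion.** The contradiction holds. The SAP's set for the primary efficacy outcome excludes every shared normal-weight participant, while the planned n of 40 requires at least 20 of them. Followed literally, the rule gives at most 20 participants, no normal-weight comparison, a fat/water predictor limited to overweight and obese adults, and half the participants per regression predictor.

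The consequence for Aim 1 power is modest and conditional. With d = 1.5, 80% still holds for most splits of 20. It is missed only with marked imbalance: at 14:6 under Mann-Whitney, and at 15:5 under both tests, as would happen if prevalence were near the quoted 74%. This rests on reading 4 mmol/L as the within-group SD, on normal data, and on an assumed prevalence.

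The case for correction rests on the conflicting population definitions more than on power. It should be corrected because the SAP must fix who is analysed, and correcting it is nearly free.

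**What to change.** - **SAP 6.2 and Section 10:** define the analysis population as (a) participants enrolled here with BMI 25–40, plus (b) shared IRB #151943 participants with BMI 18 to <25 who meet every criterion other than BMI and have the same diet and MRI data. Word the randomisation requirement so that it does not exclude group (b).
- **SAP 6.1 and Protocol 9.0:** state that n = 40 refers to this combined set.
- **Protocol 9.0:** change the description of the shared participants from identical criteria to identical criteria except BMI.
- **Protocol 2.0 and 3.0:** make clear that BMI 18–40 is the range analysed and BMI 25–40 the range enrolled here.

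The protocol for IRB #151943 was not supplied. The sponsor should therefore confirm that its diet and MRI data match before the wording of (b) is settled. The cost is a few sentences in each document; no new participants or procedures are needed.

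### SAP Section 10 counts only treatment-related adverse events and names only a per-protocol set for safety, so its incidence table can be incomplete

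*SAP*

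**What the plan says.** SAP Section 10 (Safety Analyses) sets four rules.

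- **Set.** The only population described is "Per-protocol all randomized subjects who have been gone through diet intervention in the study without major protocol deviations". A deviation is major if it could affect how the efficacy results are read. The section then adds: "Data will be used for the primary efficacy outcome and safety analysis".
- **Timing of the criteria.** "Detailed protocol deviation criteria will be determined at the latest before database lock".
- **Counting and denominator.** Each subject counts once, for adverse events overall "or any sub-classification thereof by treatment, time period, severity, etc", and "the denominator will be the total population size".
- **Filter.** "Only incidence of AEs that are judged to be related to the treatment will be reported".

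SAP Section 6.3 gives the setting: "the order of the study interventions will be randomized using a randomized crossover design", and "This is not a blinded study".

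The protocol is broader. Section 6.0 has all subjects monitored for adverse effects. Section 7.0 has a severity scale from 0 to 5, a six-monthly summary of any adverse event to the IRB, and reporting of all adverse events at continuing review. Section 8.0 lists a significant adverse event among the reasons for discontinuation. Section 4.0 enrols 20 subjects. Neither document defines a safety set of all randomised or all exposed subjects.

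**The concern.** An adverse event table should show how many of the subjects put through the study had an event, whatever its presumed cause. Two rules in Section 10 prevent that.

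The first makes inclusion depend on a causality judgement. The people making it know which diet the subject is on, and neither document gives criteria for it. The second borrows an efficacy population for safety. Subjects leave that population for reasons tied to efficacy, under criteria that may be fixed after the data have been seen. Subjects who deviate or stop early are also those whose events one would most want to see.

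The denominator phrase does not settle the matter, because the population it refers to is not named. A reader of the finished table could not tell what was left out.

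**Working it through.** The plan states no adverse event rate, safety-set size or expected incidence, so there is no figure to reproduce. The event counts below are assumptions that show direction and scale only.

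**Inputs.** N = 20 randomised (protocol Section 4.0). Assumed: a = 3 subjects with at least one event, so the all-subject incidence is a/N = 3/20 = 15.0%.

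**1. Related-only filter.** Let r be the number of those subjects with at least one event judged related. Reported incidence = r/N.

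| r | Reported |
|---|---|
| 3 | 3/20 = 15.0% |
| 2 | 2/20 = 10.0% |
| 1 | 1/20 = 5.0% |
| 0 | 0/20 = 0.0% |

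Since r cannot exceed a, the filter can lower the incidence but never raise it.

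**2. Per-protocol restriction, without the filter.** Remove one subject from both numerator and denominator.

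- The subject had an event: (a − 1)/(N − 1) = 2/19 = 10.5%, a fall of 4.5 points.
- The subject had no event: a/(N − 1) = 3/19 = 15.8%, a rise of 0.8 points.

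The direction depends on who is removed.

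**3. Undefined denominator.** Suppose events are counted only in the 19 per-protocol subjects, but the total population is read as the 20 randomised. The two results become 2/20 = 10.0% instead of 10.5%, and 3/20 = 15.0% instead of 15.8%. In this illustration the ambiguity is worth 0.5 to 0.8 points, less than the loss of one subject with an event.

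**4. What *treatment* covers.** Section 10 does not define it. SAP Section 8.2 describes treatment compliance in terms of the diet intervention, and protocol Section 8.0 names treatment and procedures as separate things. Both point to the diets. On that reading, the risks that protocol Section 6.0 lists for blood draws (pain, allergic reaction, infection, bleeding) and for the scanner (confinement, claustrophobia) fall outside the reported incidence even when a study procedure plainly caused them.

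**5. Who leaves the set.** Subjects with major deviations clearly do. Whether a subject who stops early for an adverse event also does is uncertain. Having gone through the diet intervention may mean both diets or any diet, and the list of criteria that follows is garbled, with what looks like a heading run into it as a third item.

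**The case against.** The best defence is that little is at stake. No aim or endpoint concerns safety. The IRB receives all adverse events without this filter, and SAP Section 8 says that data will generally be listed. Events judged unrelated are therefore not lost to the study; one descriptive table omits them. This stands, and it sets the severity. It does not repair the table: IRB reporting does not define the statistical summary, and a listing is not an incidence with a denominator.

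It can also be said that protocol Section 7.0 defers to IRB policies, which may contain relatedness criteria not visible here. That is possible, but criteria would only make the filter more consistent. Unrelated events would still be missing.

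Some stronger readings are tempting and are not supported:

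- *The table must understate incidence.* True of the filter, not of the per-protocol restriction, which can raise it (step 2).
- *The denominator takes in the shared normal-weight cohort and so dilutes the rates.* Protocol Section 9.0 shares those data for the study hypotheses and the weight comparison. Nothing sets events from this protocol's subjects over a denominator that includes the other cohort.
- *The by-period rows are already wrong for subjects who leave before the second diet.* If the total is the per-protocol set, and membership means both diets were taken, no such subject is in it. The problem arises only with a wider set.
- *Subjects who stop for an adverse event are certainly excluded.* The wording is too unclear to say.

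**Conclusion.** The point holds in a limited form. Followed as written, Section 10 gives an adverse event summary without any event judged unrelated, and without the events of subjects removed from the per-protocol set. If *treatment* means the diets, blood-draw and scanner events are missing too. The denominator needs to be tied to a named set.

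The size cannot be stated, because it depends on event counts, relatedness judgements and deviation criteria that the documents do not give. With 20 subjects, a single exclusion can shift the result by several points, as in the assumed case of 15.0% against 10.5%. Severity is low, and the defect is confined to this one summary. It is still worth correcting, because it comes from explicit rules rather than missing detail and is cheap to remove.

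**What to change.** In SAP Section 10:

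1. Define the safety set as all subjects randomised under this protocol, and confine the per-protocol set to efficacy. No exposure condition is needed, since protocol Section 5.0 describes the screening blood draw before randomisation.
2. Report the incidence of all adverse events by diet or period at onset (baseline, each diet, washout, MRI). Show related events as a subset row, stating whether they are related to diet or to a procedure. List separately any event at screening, including in consented subjects who were not randomised.
3. Use the safety set as the overall denominator, and the number who entered each diet or period for by-period rows. The wider safety set makes this necessary, because it can include subjects who never reach the second diet.

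The cost is SAP wording and one small table. Both schedules already collect adverse events at the baseline, Diet 1, washout and Diet 2 visits.

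As separate housekeeping, reconcile the adverse event rows of the two schedules. The protocol appendix marks screening but not the MRI visit; SAP Section 6.4 marks the MRI visit but not screening.
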